4.9 Risk, Safety, and Indications/Contraindications

Both the Deltex Medical CardioQ-EDM (Deltex Medical Limited; K172457; June 28, 2018), and the CipherOx CRI, (Flashback Technologies, Inc.; K173929; July 24, 2018), have been cleared through Class II/Traditional 510(k)s.

The CardioQ-EDM has been used in over 400,000 patients worldwide. To date, there have been no serious adverse events associated with EDM. Extrapolating data from nasogastric tube and transesophageal echocardiography probe placement, the incidence of esophageal perforation is exceedingly low and only described in case reports and small case series. Nonetheless, the risk of esophageal perforation will be discussed during the informed consent process. The co-investigator in the operating room will be responsible for reporting any adverse events to the PI. In the event of an adverse event, the PI will fully disclose details to the participants family, COMIRB, Children's Hospital Research Institute, and Deltex Medical.

To minimize risk associated with CardioQ-EDM placement, the PI or Co-investigators (Drs. [name] or [name]) who all have experience placing similar objects will place the device by applying jaw thrust in the standard fashion. Proper positioning of the device will be confirmed by Doppler waveform, negating the need for radiographic confirmation. Specific pediatric CardioQ-EDM probes (KDP72) which are indicated in children age 15 and younger will be placed through the oral cavity. Although the device has not been used at CHCO previously, the insertion is identical to an orogastric tube placement and thus the investigators do not believe that a bioengineering review is necessary.

One additional risk is the potential for extubation with probe manipulation. To minimize this risk, probes will be placed while the anesthesiologist maintains the airway. If at any point during the case, the probe becomes mal-positioned, no repositioning will be performed, and the study is terminated for this individual in an effort to avoid inadvertent extubation. Furthermore, the probe

Protocol #: 18-2513

PI: [name]

Version date: 07/01/2019

will remain in place until the time of extubation to again minimize the risk of inadvertent extubation.

The CipherOx-CRI probe was cleared by the FDA for patients with a finger thickness of 0.3 to 1 inch. There were no warnings, precautions or contraindications in the product brochure.

4.9.1 CardioQ-EDM Details

- The Deltex Medical Doppler KDP72 probe is for use in patients aged 15 years or younger for up to 72 hours.
- The KDP probe is 28 in (72 cm) long and has maximum usage time which is defined on the probe packaging.
- It is only approved for ORAL placement into the esophagus of a single patient over 5.5 lb. (2.5 kg) in weight.
- The patient should be under full sedation or general anesthesia.
- The probe shaft has six depth markers visible through the transparent cover starting at 6 in (15 cm) through to 16 in (40 cm) incrementing in steps of 2 in (5 cm). These markers act as a guide to facilitate correct probe placement.
- Nasal placement of any probes in patients aged 15 years or younger is not approved nor is usage of the CardioQ-EDM for patients below 5.5 lb. (2.5 kg) in weight.

4.9.2 CardioQ-EDM Contraindications

- Doppler probes (DP240 and I2n) should not be placed in patients under 16 years of age. We will be using the KDP72 probe
- Do not use where nasal injuries are apparent or may have occurred.
- Do not use where nasal polyps exist.
- Do not use where there are circumstances of facial trauma.
- Do not use where there is a risk of brain injury.
- Do not use in patients undergoing intra-aortic balloon pumping.
- Do not use with carcinoma of the pharynx, larynx or esophagus.
- Do not use with aneurysms of the thoracic aorta.
- Do not use with tissue necrosis of the esophagus or nasal passage.
- Do not use in close proximity to laser surgery.
- Do not use in patients with pharyngo-oesophago-gastric pathology and/or severe bleeding diatheses.

5. Specific Aims:

Aim I: Define fluid responders based on aortic ΔV_{peak} : Among infants undergoing cranial vault reconstruction for craniosynostosis, we aim to determine the proportion who respond to clinically administered fluid or blood products defined by pre- and post-fluid challenge EDM $\Delta V_{Peak} >10\%$.

Mock-up Table 1: Demographics of Responders and Non-Responders to Initial 10 mL/kg bolus prior to surgical incision

Variable	Responders	Non-Responders	P-value
Demographics			
Age			
Weight			
Height			
BMI			
Gender			
Ethnicity			
Duration of NPO status			
Associated syndrome			

Legend: BMI, body mass index; npo, nil per os

Aim II: Calculate the PPV, NPV, sensitivity, specificity, and optimal threshold for CRI and collapsibility index as tools to prediction fluid responder

Protocol #: 18-2513

PI: [name]

[figure not shown]
Version date: 07/01/2019

		Fluid Responsive	
		Yes	No
CRI Threshold	+	True Positive	False Positive
	-	False Negative	True Negative

		Fluid Responsive	
		Yes	No
CI Threshold ($\geq 15\%$)	+	True Positive	False Positive
	-	False Negative	True Negative

Performance will also be calculated for heart rate, systolic blood pressure, mean arterial pressure, pulse pressure variability and stroke volume variability. Two separate analyses will be performed – one for the 10 ml/kg protocolized bolus provided immediately after induction and one accounting for all boluses provided.

Mock-up Figure

Mock-up Table 2 – Performance at predicting fluid responsiveness

Variable	Correlation (r)	AUC
IVC CI		
CRI		
SBP		
PPV		
SVV		
MAP		
HR		

Protocol #: 18-2513

PI: [name]

Version date: 07/01/2019

Aim III: Evaluate confounding variables that may influence CRI or collapsibility index

Variable	Scale of Measurement	Data Point Location	Analysis Method
Outcome Variable IVC CI, CRI, PPV, SVV, HR, SBP, MAP AUROC	Interval	Pre-bolus measurements	
Confounding Variables Age Weight BMI Gender Ethnicity Associated syndrome Preoperative Hemoglobin Duration of NPO status Core temperature at time of bolus Paralysis provided (Y/N) Blood transfusion (Y/N) Total blood volume Total Crystalloid Total Colloid Vasopressor requirement Total amount of vasopressor Ventilation Tidal volume PEEP PIP Spontaneous breaths	Interval Interval Interval Dichotomous Ordinal Dichotomous Interval Interval Interval Dichotomous Dichotomous Interval Interval Interval Dichotomous Interval Interval Dichotomous	Demographics Demographics Demographics Demographics Demographics Demographics Demographics Preop results Anesthesia Rec Anesthesia Rec Ventilator Ventilator Ventilator Ventilator	Multivariable Linear Regression

Figure or Table will depend on results found. If neither of the outcome variables are affected by the confounding variables may only report this finding in the text.

Two separate analyses will be performed – one for the 10 ml/kg protocolized bolus provided immediately after induction and one accounting for all boluses provided.

Protocol #: 18-2513

PI: [name]

Version date: 07/01/2019

Reference:

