While numerous tools are available to guide resuscitation, one potential benefit of this project is to validate the use of CipherOx-CRI in this cohort. If CRI proves to be a valuable predictor of intravascular volume status and the need for volume expansion, this could negate the need for arterial line placement which is time consuming, invasive, and associated with complications such as arterial thrombosis. Furthermore, after validation in this cohort, additional studies could be performed in other groups of children at risk for hemorrhagic shock in the hopes to guide ongoing resuscitation accurately without the need for invasive devices.

3. Specific Aims and Hypotheses:

Aim I: Among infants undergoing cranial vault reconstruction for craniosynostosis, we aim to determine the proportion who respond to clinically administered fluid or blood products defined by pre- and post-fluid challenge $\Delta V_{Peak} > 10\%$.

Hypothesis Ia: We hypothesize that approximately half of the cohort will be fluid responsive defined by ΔV_{Peak} by $> 10\%$ after a 10 mL/kg fluid bolus is administered immediately following induction. Although this is a prediction, it is based on previous published reports suggesting a relatively even distribution among patients who clinicians believe need volume expansion. Additionally, because these children have a mean weight of 6.4 kg and will have been nil per os for several hours prior to surgery, they are at risk for intravascular volume depletion even prior to blood loss.

Hypothesis Ib: Because clinicians use pulse pressure variability, heart rate, systolic blood pressure, urine output, and blood loss to gauge need for ongoing resuscitation (either crystalloid, colloid, or blood), we suspect that more than half of subsequent fluid challenges will be given to infants who are fluid responsive (defined by a pre- and post-bolus ΔV_{Peak} of $> 10\%$).

Aim II: To determine the PPV, NPV, sensitivity, specificity, and optimal threshold for CRI, collapsibility index, pulse pressure variability, stroke volume variability, heart rate, systolic blood pressure, and mean arterial pressure as tools to predict fluid responsiveness using pre- and post-fluid challenge $\Delta V_{Peak} > 10\%$ to define fluid responders.

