4.8 Data Analysis

Protocol #: 18-2513

PI: [name]

Version date: 07/01/2019

Univariate comparisons between various measures will be compared between the fluid responder and non-responder groups using t-tests or Fisher's exact test for continuous and categorical measures, respectively. Area under the curve will be calculated for CI and CRI using both simple logistic regression models including no confounders and multiple logistic regression models including confounders. Confounders will be identified for inclusion in the multiple logistic regression models by calculating the univariate association with the gold standard (using a $p < 0.10$ threshold). These adjusted models will be used to verify thresholds for classification using CI and CRI which will then be applied to calculate classification summary measures (e.g., PPV, NPV, sensitivity, and specificity). Data analysis will be performed by a biostatistician funded by the Division of Pediatric Surgery using R and SAS statistical software programs.

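### Aim II does not say whether the IVC collapsibility index is classified at a fixed 15% or at a data-derived optimum, and plans no correction for optimism in thresholds chosen and scored on the same children

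*Combined protocol and SAP*

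**What the plan says.** Three places in the combined protocol and SAP bear on the threshold.

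- **Section 3, Aim II** sets the objective: "To determine the PPV, NPV, sensitivity, specificity, and optimal threshold for CRI, collapsibility index, pulse pressure variability, stroke volume variability, heart rate", followed by systolic and mean arterial pressure. An optimal threshold is therefore wanted for all seven indices, CI included.
- **Section 5, Aim II** repeats this for the two new devices: "Calculate the PPV, NPV, sensitivity, specificity, and optimal threshold for CRI and collapsibility index as tools to prediction fluid responder". Two 2x2 tables follow. One row label is "CRI Threshold" with no number; the other is "CI Threshold ($\geq 15", that is, CI of at least 15%. No source for 15% is given there or elsewhere in the supplied text. The section adds: "Performance will also be calculated for heart rate, systolic blood pressure, mean arterial pressure, pulse pressure variability and stroke volume variability". No cut-offs are given for those five.
- **Section 4.8, Data Analysis** says adjusted logistic models will be used to "verify thresholds for classification using CI and CRI which will then be applied to calculate classification summary measures". It names no selection criterion, does not mention 15%, and gives no threshold rule for the five comparators.

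Separately, Hypothesis II is framed as an AUROC of about 0.9 for CRI and CI, and mock-up Table 2 lists correlation and AUC for all seven indices. Neither needs a cut-off.

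**The concern.** A cut found from the data and a cut fixed at 15% will in general give different sensitivity, specificity and predictive values for CI from the same children. These four measures are named outputs of Aim II, and the plan does not say which cut produces them. Left open until the data are in, the choice could be made after seeing which cut looks better.

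Each way of settling it has a consequence. If every index is cut at its own best point in these children and then scored on them, every index looks better than it would in new children, and no internal validation or optimism correction is planned. If CI alone stays at 15% while the others are optimised, CI is scored without that advantage and its threshold-based measures cannot fairly be set beside theirs. The background section hopes that CRI or CI could replace arterial lines in guiding fluid, so the credibility of error rates at a usable cut-off matters.

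**Working it through.** **Side-by-side reading.** Section 3 wants an optimum for CI. The Section 5 aim wants an optimum for CI. The Section 5 table prints 15% for CI and leaves CRI open. Section 4.8 verifies thresholds from adjusted models. That verb could mean checking a preset value, but CRI has none to check. A cut from a multiple logistic model also acts on predicted probability, not on CI itself, so it is a possible third version. No text ranks these.

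**Plan's own figure.** The supplied text states no sample size, sensitivity or specificity, so there is nothing to reproduce. The calculation below is illustrative.

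**Inputs**
- Responder fraction 0.5: Hypothesis Ia expects about half.
- AUC 0.9: Hypothesis II, for CRI and CI. AUC 0.7 and 0.8 are assumed for weaker indices, and 0.5 for a useless one.
- N = 20, 30, 60: assumed. Thirty is the number of probes in Section 4.2, not a stated sample size.
- Normal distributions with equal variance, and the Youden rule: assumed.

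**Formulas.** Non-responders follow N(0,1) and responders N(d,1), with d = √2 × z(AUC). The Youden index is J = sensitivity + specificity - 1. The best fixed cut is d/2, with population J = 2Φ(d/2) - 1. For AUC 0.9, d = 1.414 × 1.2816 = 1.812 and J = 2Φ(0.906) - 1 = 0.635.

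**Simulation** (10,000 data sets per cell). Choose the cut that maximises J in the sample. Record its apparent J, then its true J on the generating distributions. Optimism is the difference.

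| N | AUC | Apparent J | True J at chosen cut | Optimism |
|---|---|---|---|---|
| 20 | 0.7 | 0.459 | 0.247 | 0.212 |
| 20 | 0.8 | 0.593 | 0.401 | 0.192 |
| 20 | 0.9 | 0.750 | 0.588 | 0.162 |
| 30 | 0.7 | 0.428 | 0.254 | 0.174 |
| 30 | 0.8 | 0.565 | 0.410 | 0.155 |
| 30 | 0.9 | 0.730 | 0.600 | 0.130 |
| 60 | 0.7 | 0.384 | 0.262 | 0.122 |
| 60 | 0.8 | 0.528 | 0.423 | 0.105 |
| 60 | 0.9 | 0.700 | 0.612 | 0.088 |

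A repeat with 40,000 data sets per cell, at these N and AUC values, agreed within 0.003. At N = 30 and AUC 0.9, 0.130 / 2 = 0.065, or about 6.5 points on average on each of sensitivity and specificity. A useless index (AUC 0.5) shows an apparent J of 0.20 at N = 30.

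**Mixed rule: CI fixed, others optimised.** Here the relevant gap is apparent J at the in-sample cut minus J at a fixed cut. At AUC 0.9, with the fixed cut at the true optimum:
- N = 20: 0.750 - 0.638 = 0.112
- N = 30: 0.730 - 0.638 = 0.092
- N = 60: 0.700 - 0.636 = 0.064

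If the fixed cut lies 0.5 SD or 1 SD from the optimum, its J falls to 0.578 or 0.434. At N = 30 the gap widens to 0.730 - 0.578 = 0.152 or 0.730 - 0.434 = 0.296. The documents do not show where 15% falls on this scale.

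**The case against.** The 15% appears once, in brackets, as a row label in a table shell. It is absent from the definitions in Section 4.4 and from Section 4.8, and may be only a placeholder. Aim II lists the optimal threshold as one output beside sensitivity, specificity and the predictive values, so accuracy at 15% plus a separately reported optimum would fit its wording. This stands as far as it goes: the fault may be a missing clarification and not two rules both intended. It does not remove the gap, because nothing tells the analyst which reading to follow.

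Three stronger readings are tempting and are not supported:

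- *That Section 4.8 prescribes a data-derived optimum and so contradicts the 15%.* It speaks only of verifying thresholds, which also fits checking a preset value. It is ambiguous.
- *That the accuracy of CI as a whole is undefined, or that the indices cannot be compared.* Hypothesis II and mock-up Table 2 rest on AUC, which does not depend on the cut-off.
- *That the plan is biased against CI.* This arises only if CI is fixed and the others optimised, and no section says so. If all are optimised by one rule, that particular imbalance disappears, though optimism remains.

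It is also fair that the optimism figures describe in-sample cut selection in general, and that they depend on an assumed sample size. Nor is a fixed cut automatically safer: it avoids selection optimism but loses accuracy if misplaced.

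**Conclusion.** The point holds for the threshold-based measures only. The plan asks for an optimal CI threshold and also prints a fixed one without a source, and Section 4.8 does not reconcile them. Where optimal cuts are used, the plan implies choosing and scoring them on the same children without correction. Over 20 to 60 children this overstates sensitivity + specificity by roughly 0.09 to 0.16 at AUC 0.9 and 0.12 to 0.21 at AUC 0.7. These sizes rest on the binormal model, the Youden rule, equal groups and one bolus per child, none of which the plan fixes as the basis for thresholds. Only the direction, overstatement that shrinks as the sample grows, should be taken as firm. This is an inexpensive improvement to the plan; it does not undermine the AUC analysis.

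**What to change.** 1. Reconcile Section 3, Section 4.8 and the Section 5 table: state whether 15% for CI is prespecified, giving its source, or a placeholder to be removed. The documents give no basis for choosing between these, so the investigators must say.
2. Derive thresholds for all seven indices by one named rule, for example Youden, on the index itself, and label them exploratory.
3. Report sensitivity, specificity and positive and negative predictive values at those thresholds with bootstrap optimism correction, repeating the threshold selection in each resample. Resample children, not boluses, because Section 4.4 counts boluses at least 30 minutes apart as separate events and the all-bolus analysis will contain repeats.
4. If 15% is kept, report CI accuracy at 15% separately, with exact binomial intervals, for the protocolized post-induction bolus, where each child contributes once.
5. Keep AUC as the basis for comparing indices, as mock-up Table 2 already does.

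The cost is a few sentences in Sections 4.8 and 5 and a short bootstrap program. The corrected accuracy figures will look less favourable than the uncorrected ones.

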Hypothesis II: CRI and collapsibility index will reliably predict fluid responsive patients with an approximate area under the receiver operating characteristic curve (AUROC) of 0.9 while other indices will have a lower predictive accuracy.

Aim III: Evaluate confounding variables that may influence predictive measures outlined in Aim II.

Hypothesis III: Confounding variables that may decrease the predictive accuracy of indices described in Aim II include spontaneous breathing over the ventilator, minimal blood loss, and hypothermia

4. Materials and Methods:

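### Hypothesis III is about loss of predictive accuracy, but the Aim III regression tests only whether the level of each index shifts with a factor

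*Combined protocol and SAP*

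**What the plan says.** Section 3 sets Aim III as "Evaluate confounding variables that may influence predictive measures outlined in Aim II". Hypothesis III then speaks of confounding variables that "may decrease the predictive accuracy of indices described in Aim II include spontaneous breathing over the ventilator, minimal blood loss, and hypothermia". Aim II defines the measures concerned: "To determine the PPV, NPV, sensitivity, specificity, and optimal threshold for CRI, collapsibility index, pulse pressure variability, stroke volume variability", with heart rate, systolic pressure and mean arterial pressure completing the list.

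Section 5 words the aim differently: "Evaluate confounding variables that may influence CRI or collapsibility index". The table beneath it gives the outcome row as "Outcome Variable IVC CI, CRI, PPV, SVV, HR, SBP, MAP AUROC", on an interval scale, located in the pre-bolus measurements. It lists about 20 covariates and names the method as "Multivariable Linear Regression". Core temperature and spontaneous breaths are among the covariates. Blood loss is not named; transfusion and total blood volume are. Responder status does not appear. A note below the table allows an absence of influence to be reported in the text alone.

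Section 4.8 says "Area under the curve will be calculated for CI and CRI using both simple logistic regression models" and also multiple logistic models that include confounders. On their choice it says "Confounders will be identified for inclusion in the multiple logistic regression models by calculating the univariate association with the gold standard", at p < 0.10. Section 5, Aim II, adds performance for the other five indices. Section 5 splits the Aim II and Aim III analyses one way only: the protocolized post-induction bolus, and all boluses together.

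**The concern.** Accuracy describes how well an index separates responders from non-responders. A regression of the index on a factor, without responder status, estimates how far the average index differs between factor levels. These are different quantities, and each can change without the other.

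If the plan is followed as written, a null regression could be read as showing that accuracy is unaffected, which it cannot show. A positive one would show that an index moved, without saying how much sensitivity, specificity or AUC changed, or in which direction. Either way Hypothesis III would be left largely unanswered.

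**Working it through.** The text available for review gives no sample size, power or significance level for Aim III, so there is no planned figure to reproduce. The check is a reading of the models plus an illustration.

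**Inputs from the document.** AUROC of about 0.9 for CRI and collapsibility index (Hypothesis II); about half responders (Hypothesis Ia); 30 probes (section 4.2, a count of materials and not a stated sample size).

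**Assumptions.** Boluses n = 30, 60 or 90, independent; factor present in 50% or 20% of boluses and unrelated to responder status; AUC falling to 0.70; index normal with SD 1 within responders and within non-responders.

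**Step 1: separation.** d = √2 × z(AUC), which gives 1.81 for AUC 0.90 and 0.74 for 0.70.

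**Step 2: accuracy falls, mean index unchanged.** At the midpoint cut-off, sensitivity = specificity = Φ(d/2). This falls from Φ(0.906) = 82% to Φ(0.371) = 64%. A one-factor linear model at two-sided 0.05 flags the factor in about 5%/5%/5% of simulated datasets at n = 30/60/90 with the factor in half of boluses, and in about 2%/3%/3% with the factor in 20%.

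**Step 3: level shifts by 1 SD, AUC within each level stays 0.90.** With non-responders centred at 0 and responders at 1.81, mean correct classification among boluses with the factor depends on the cut-off:

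| Cut-off | Without shift | With shift |
|---|---|---|
| 0.906 | 82% | 72% |
| 1.4 | 79% | 79% |
| 1.9 | 72% | 82% |

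So a level shift may lower accuracy at a fixed cut-off, leave it unchanged or raise it. At 0.906 the fall comes from specificity going from 82% to 46% while sensitivity rises from 82% to 97%.

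**Step 4: power of the linear model for that shift.** With one factor and equal levels it is about 49%/81%/94% at n = 30/60/90. With 19 further unrelated covariates, closer to the length of the Aim III list, it is about 18%/61%/87%.

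**Step 5: section 4.8.** It computes AUC for two of the seven indices and mentions no interaction between index and factor. In a large simulated sample where the factor lowers AUC from 0.90 to 0.60 with no mean shift, the AUC is 0.765 for the index alone and 0.765 with the factor added as a covariate, so comparing unadjusted with adjusted AUC reveals nothing. Because selection rests on association with responder status, such a factor passed a p < 0.10 Fisher screen in only 5% to 9% of samples of 30 to 90.

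**Step 6: precision of the alternative.** The Hanley-McNeil variance of an AUC of size A is [A(1−A) + (n₁−1)(a−A²) + (n₀−1)(b−A²)]/(n₁n₀), with a = A/(2−A) and b = 2A²/(1+A). For n = 30 and equal levels, n₁ = n₀ = 7.5 in each level. The standard errors are 0.139 (AUC 0.70) and 0.086 (AUC 0.90), so the difference has standard error √(0.139² + 0.086²) = 0.164 and a 95% half-width of 1.96 × 0.164 = 0.32. In full:

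| Factor in | n = 30 | n = 60 | n = 90 |
|---|---|---|---|
| 50% of boluses | 0.32 | 0.22 | 0.18 |
| 20% of boluses | 0.47 | 0.32 | 0.26 |

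Several boluses per child may widen these further.

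**The case against.** A reader might infer that no planned analysis looks at accuracy by level of any Hypothesis III factor. The document does not support that. The post-induction bolus is analysed separately, and section 4.7 and the first mock-up table place it before incision. It therefore gives accuracy, for all seven indices, with essentially no surgical blood loss, and this stands as a partial answer. It remains partial because its comparator, all boluses, contains the same boluses, because it is not presented as a test of Hypothesis III, and because it does not address spontaneous breathing or hypothermia.

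A second objection is that AUROC stands in the outcome row, so accuracy was probably intended, and that the broken layout may hide a separate method for it. The intention is likely. But AUROC is one number per index per analysis, so it cannot be regressed on bolus-level covariates by the method named, and no other method is legible.

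A third is that the blind case in step 2 is special: responders and non-responders must move towards each other equally. That is fair. If only responders are blunted, with the same drop in AUC, the one-factor linear model flags it in about 21%/40%/53% of datasets (about 10%/28%/44% with 19 added covariates). The regression is thus not uninformative, but even then it reports a difference in level and not a loss of accuracy.

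Finally, accuracy by level will be imprecise. At n = 30 the half-width exceeds the assumed drop of 0.20. This argues for calling the aim exploratory. It does not make a regression of level answer the hypothesis.

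**Conclusion.** The point holds in this form: the linear regression planned for Aim III addresses shifts in index level, and Hypothesis III asks about accuracy. Section 4.8 does not fill the gap, and the pre-incision bolus analysis fills it only in part, for blood loss.

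In the illustration, a fall in sensitivity and specificity from 82% to 64% each would be flagged no more often than chance if the mean index is unchanged. A 1 SD shift could move correct classification from 82% to 72%, or the other way, depending on the cut-off. These sizes rest on the assumed number of boluses, factor frequency, size of drop and normal model. The mismatch itself rests on the text alone.

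Two limits apply. The Aim III table is read from a broken layout, and two parts of the document were not available for review. A reader might also infer that Aims I and II are undermined, or that any shift in level means lost accuracy. Neither follows: this point leaves the analyses of Aims I and II as they are, and step 3 shows that accuracy can stay the same or rise.

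**What to change.** Before the data are analysed:

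- For each Hypothesis III factor, with levels set in advance, report every Aim II index's AUC, and its sensitivity and specificity at the same chosen threshold, by factor level with 95% confidence intervals. In the all-bolus analysis, use a bootstrap that resamples children.
- Give responder and non-responder counts in each level, and only the counts where a level is too sparse for an AUC.
- For blood loss, compare the post-induction bolus with later boluses only, so that the groups do not overlap. Confirm that blood loss is recorded on the data collection form.
- Use the same wording for Aim III in sections 3 and 5, and label it exploratory.
- Keep the linear regression as a description of level shifts, remove AUROC as its outcome, and do not report a null result from it as no effect on accuracy.

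The cost is a change of wording and a little more analysis of data largely already planned. The downside is wide intervals, as in step 6, which should be shown and not replaced by a significance test.
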